23-25	
Schedule of Events
 
 Study table has been modified to eliminate the Part A screening period, add relevant evaluations to Day 1, and to separate out Part A Arms to clarify that safety monitoring activities will not be done on Part A non-treatment Arm 2 (includes adverse event recording, lab testing, and ECG's). Adds reference that both serum and urine pregnancy tests are allowed. Adds clarification to footnote language regarding assessments and questionnaires done on Days 1 and 8 are to be done prior to dispensing drug. This allows for dosing of drug by subjects prior to study visit on Day 8. Clarifies that clinically significant abnormal labs will be repeated until normalized to allow for lab values that may present as abnormal but not clinically significant. Adds reference to remote or in-person clinic visits for the Part A Arm 2 non-treatment group for visits Days 8 and 21.
24	

	
 Clarifies that correlative labs collected includes biomarkers.
19 19 20	
Outcomes & Study Tools
 
 Removal of screening period language for Part A. Added for clarity that language applies to both acute and sub-acute concussions. Corrects visit dates for BrainCheck testing to match what was previously listed in the Schedule of Events.
21	
Statistical Analysis—Removes reference to baseline visit for emphasis that there is not a screening period.

Ghrelin (OXE--103) for acute concussion management

HSC #: 145983

Site Investigators: [name] (PI), [name] (Co-I), [name] (Co-I), [name] (Co-I), [name] (Co-I)

Summary:

Ghrelin is a naturally occurring hormonal peptide with extensive preclinical and clinical safety data to supporting the safety of OXE-103 for studies in patients with concussion/mTBI. In addition, Ghrelin has been shown in many preclinical and clinical studies to potentially target many different areas of concussive injury including energy regulation, inflammation, and axonal connectivity. There have been no clinical studies looking at ghrelin as treatment for acute concussion. If there are indeed benefits, the societal impact could be huge.

Overview

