We propose a pilot study to treat 1) Sub-acute concussion with OXE-103 in Part A and 2) Acute concussion management with OXE-103 within 24 hours of presentation to the Trauma Unit in Part B. For Part A, we will recruit subjects from the University of Kansas Health System Center for Concussion Management (CCM) clinics which include Neurology, Sports Medicine, and Neurosurgery/PM&R. For Part B, we will recruit subjects from the University of Kansas Health System Trauma Unit. In Part A we will compare an open-label treatment arm (OXE-103) to a non-treatment concurrent control arm. Part B will be randomized double blind 1:1 to treatment with OXE-103 and placebo. We will compare these using self-report symptom scoring, quality of life questionnaires, computerized cognitive testing assessing executive function, memory and processing speed, and accelerometer-based balance scoring. The exploratory nature of this study is not powered to yield statistically significant outcomes, but will allow detection of trends within subjects and between groups, will support comparison with standard tests of neurocognitive functions, and will provide sample size estimates for future studies of people with persistent concussion related symptoms.

This study is highly relevant clinically and uniquely suited to being conducted at the CCM. It will be the first to test ghrelin as therapy for sub-acute concussion.

Specific Aims:

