- 4. Describe changes between symptom burden and quality of life at different time points.** This is an exploratory aim. We will collect data at days 21 and 44 to allow for comparisons at later time points. This may be used to describe changes in these measurements at time points after administration of OXE-103. It is hypothesized that the effects of OXE-103 are long standing and therefore worsening after administration should not occur. We will have data to compare day 15 to days 21 and 44.

5. **Describe changes in cognitive performance between the two groups.** This aim defines one of our secondary objectives. Improvement in cognitive functioning could correlate with underlying improvement in neuronal function. We will assess cognitive function with BrainCheck, a digital assessment tool, at specified intervals. This tool is administered via iPad and can be administered in clinic with supervision by trial personnel as well as at home by the subject.

Benefits/Risks of research

Benefits: Currently rest is the initial treatment for concussion. Therapies that can be prescribed later (there is no consensus as to when to start these—tends to range from a couple of weeks post-injury to a couple of months) include physical/vestibular therapy (but this takes time and may provoke symptoms initially), and symptomatic treatment of symptoms with medications. The effectiveness of these drugs to provide potential treatment of underlying neurometabolic changes versus purely symptomatic relief is unknown. Further, each medication comes with potential for adverse events. Providing a safe treatment that is effective at reducing symptoms, increasing quality of life, and potentially providing treatment for underlying neurometabolic dysfunction would be innovative and change the current paradigm of concussion care.

Risks: Previous studies have shown that OXE-103 is quite safe. This study will help to confirm that safety profile in this clinical population. Long term use of ghrelin can lead to increased appetite, weight gain, and adiposity [16]. However, we will mitigate that risk by using OXE-103 for a short period and we will obtain weight measurements at regular intervals during drug treatment.

Inclusion/Exclusion:

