Pre-clinical studies performed with OXE-103 showed that, continuous IV infusion of OXE-103 (up to 1000 µg/kg/hr) in conscious, unrestrained monkeys resulted in a transient increase and then decrease in blood pressure in 1 of the 4 monkeys evaluated. None of the animals had changes in heart rate, ECG parameters, respiratory rate, arterial blood pH, blood gas tensions, hemoglobin oxygen saturation, body temperature or clinical signs.

Additionally, results from the Phase 2 study as noted in Oxeia's Investigator's Brochure showed no clinically meaningful changes with regard to ECG and subcutaneous treatment with OXE-103. Results are summarized on Table 5.9 of the Investigator's Brochure, which can be cross referenced under Oxeia's existing IND (120694).

All participants will have vital signs, including heart rate and blood pressure, monitored at each clinical visit. Further, an ECG will be acquired at visits 1 through 4. This will be acquired using AliveCor's Kardiastation digital 6 lead ECG. Kardiastation is a Class II medical device cleared by the FDA for acquiring ECGs in the physician office. Kardiastation uses a HIPPA compliant smartphone app and cloud based database for storage of ECGs. ECG parameters evaluated and captured in the study database will include RR, PR, QRS, and QT intervals as well as normal sinus rhythm. Any clinically significant ECG finding will be recorded as an AE. ECG recording will not be collected for subjects in the Non-Treatment concurrent control arm Part A (Part A Arm 2).

Laboratory and Endocrine Risks:

The semi-synthetic human ghrelin to be used in the clinical study is identical to human physiologic ghrelin. Under the original sponsor of the IND, this molecule was extensively characterized in both young adults and the older adult populations under 9 clinical studies and was found to be very safe. The information is summarized in the table above. Please note the additional PD biomarker marker data included that was not referenced in the Investigator Brochure. The longest duration study of the completed studies was ASBI307 in which 151 subjects were given one of two doses BID of OXE103 for 12 weeks at the same dose level as this study. The current study is substantially shorter at 14 days of treatment.

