The study team will retain any research and data records for 5 years in accordance with institution and federal requirements, as applicable. Records will be maintained in a secure method, with restricted or limited access to only authorized individuals. Records will be kept in a locked file cabinet inside a locked office.

Part A Study Design - Schedule of events
Arm 1 (OXE-103)

Assessment	Day						
	1	4	8 +/-1	11	15	21 +/-1	44 +/-3
Clinic Visit	1		2		3	4	5
Informed Consent	X						
Inclusion/ Exclusion Criteria	X						
Demographics	X						
Body Weight	X		X		X		X
Vital signs (temperature, heart rate, blood pressure)	X		X		X		X
Medical History, including current TBI injury, mental health diagnoses, and neurologic conditions (including any cognitive dysfunction)	X						
Adverse Effects	X	X	X	X	X	X	X
Prior Medications/Therapy Hx	X						
Physical Examination	X		X		X	X	X
Neurological Examination	X		X		X	X	X
Concomitant Medications	X		X		X	X	X
ECG	X		X		X	X	
Labs: serum/urine pregnancy test	X						
Labs: CMP & CBC ¹	X		X		X	X	
Labs: PK sampling, anti-ghrelin anti-body and biomarker	X		X		X	X	
Train subcutaneous injection	X						
PCSS	X	X	X	X	X	X	X
Ipad Neurocog and balance (BrainCheck)	X	X	X	X	X	X	X
QOL - QOLIBRI	X	X	X	X	X	X	X
QOL - PGAS VAS	X	X	X	X	X	X	X
PHQ-9	X		X		X		X
Administer OXE-103 40ug/kg OR placebo SC BID **	X Study Days 1-14						
Phone Only (no in-person required)		X		X			
<hr/>							
¹ If there are any clinically significant abnormal values that have not yet corrected at Day 15, labs will be repeated at 7-day intervals until they normalize.							
**Assessments and questionnaires performed and collected on Day 1 & 8 will be completed prior to dispensing of OXE-103.							

Part A Study Design - Schedule of events
Arm 2 (Non-treatment concurrent control group)

Assessment	Day						
	1	4	8 +/-1	11	15	21 +/-1	44 +/-3
Clinic Visit	1				2		3
Remote Testing Only (No Visit)		X		X			
Remote Visit OR Clinic Visit			X			X	
Informed Consent	X						
Inclusion/ Exclusion Criteria	X						
Demographics	X						
Body Weight	X				X		X
Vital signs (temperature, heart rate, blood pressure)	X				X		X
Medical History, including current TBI injury, mental health diagnoses, and neurologic conditions (including any cognitive dysfunction)	X						
Prior Medications/Therapy Hx	X						
Physical Examination	X				X		X
Neurological Examination	X				X		X
Concomitant Medications	X				X		X
Labs: PK sampling, anti-ghrelin anti-body and biomarker	X				X		X
PCSS	X	X	X	X	X	X	X

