5.2 Secondary Efficacy Outcome Measures

- Change from baseline in QOLIBRI total score at each post-baseline assessment (Days 4, 8, 11, 15, 21 and 44)
- Change from baseline in PGAS VAS at each post-baseline assessment (Days 4, 8, 11, 15, 21 and 44)
- Change from baseline in BrainCheck composite score at each post-baseline assessment (Days 4, 8, 11, 15, 21 and 44)

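### In Part A, the between-arm BrainCheck differences on Days 8 and 21 can mix treatment with testing setting, by an unknown amount and in an unknown direction

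*Protocol*

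**What the plan says.** The Proposed Clinical Trial section of the protocol states: "In Part A we will compare an open-label treatment arm (OXE-103) to a non-treatment concurrent control arm". The two Part A schedules of events then set different visit types.

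- **Arm 1 (OXE-103):** numbered clinic visits on Days 1, 8, 15, 21 and 44; telephone contact on Days 4 and 11. Days 8 and 21 carry safety laboratory tests, and under Cardiovascular and Respiratory Risks "an ECG will be acquired at visits 1 through 4", which are Days 1, 8, 15 and 21.
- **Arm 2 (non-treatment control):** clinic visits on Days 1, 15 and 44; remote testing without a visit on Days 4 and 11; and on Days 8 and 21 a "Remote Visit OR Clinic Visit". The Recruitment section leaves telemedicine to the investigator's discretion for the control group, except on Days 1, 15 and 44. It labels that group Arm 1, but its own parenthesis and the schedule show that Arm 2 is meant.

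BrainCheck is scheduled on all seven assessment days in both arms. Under Specific Aims, Aim 5, it "can be administered in clinic with supervision by trial personnel as well as at home by the subject". SAP section 5.2 makes change from baseline in the BrainCheck composite score a secondary measure at each of the six post-baseline days. SAP section 6.8 summarises by treatment group and visit and plots both groups on one figure, and SAP section 6.13 rules out covariate adjustment. Neither document asks for the mode of testing to be recorded.

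**The concern.** BrainCheck includes reaction-time, attention, memory and balance tasks, where supervision and surroundings could plausibly matter. If one arm is tested in clinic and part of the other at home on the same study day, the difference in mean change has two sources that the data cannot separate. BrainCheck is also the only efficacy measure in the SAP that is not self-reported, so readers of an open-label comparison may lean on it. The pilot is meant to inform endpoints and power calculations for later trials, so a distorted difference on these days could be carried forward.

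The mode cannot be recovered afterwards from the app: the protocol limits what it transmits to subject code, responses and timestamps, without location.

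**Working it through.** The documents give no planned difference, SD, alpha or power, so there is no figure to reproduce. The check is a day-by-day comparison of the two Part A schedules, followed by an illustration on stated assumptions.

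**Step 1. Setting by day, from the visit rows.**

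| Day | Arm 1 | Arm 2 | Same setting? |
|---|---|---|---|
| 1 (baseline) | clinic | clinic | yes |
| 4 | remote (phone) | remote | yes |
| 8 | clinic | remote or clinic | not assured |
| 11 | remote (phone) | remote | yes |
| 15 | clinic | clinic | yes |
| 21 | clinic | remote or clinic | not assured |
| 44 | clinic | clinic | yes |

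Arm 1 is in clinic at 5 of 7 assessments and Arm 2 at between 3 and 5 of 7. The setting can differ by arm at 2 of the 6 post-baseline assessments.

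**Step 2. What reaches the arm difference.** Let s be the shift in the score when the test is taken remotely rather than in clinic (either sign), and f the share of controls tested remotely that day. Both arms have a clinic baseline, so taking change from baseline does not remove s.

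- Days 8 and 21: expected difference (Arm 1 minus Arm 2) = treatment difference − f × s.
- Days 4 and 11: s enters both arms and cancels, if it is the same in both.
- Days 15 and 44: s enters neither arm.

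**Step 3. Size, on assumed values.** Work in units of the SD of the change score, with the target of 20 completers per arm from General study design.

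- SE of a difference in means = √(2/20) = 0.316 SD.
- 95% half-width = 1.96 × 0.316 = 0.62 SD.
- Size of the distortion: b = f × d, where d is the absolute value of s.
- Chance that a two-sided 95% interval excludes zero when treatment has no effect = Φ(b/SE − 1.96) + Φ(−b/SE − 1.96).

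| f (assumed) | d (assumed) | b, in SD | b/SE | Chance of excluding zero |
|---|---|---|---|---|
| 0.25 | 0.1 | 0.025 | 0.08 | 5.1% |
| 0.5 | 0.3 | 0.15 | 0.47 | 7.6% |
| 1.0 | 0.1 | 0.10 | 0.32 | 6.2% |
| 1.0 | 0.3 | 0.30 | 0.95 | 15.8% |
| 1.0 | 0.5 | 0.50 | 1.58 | 35.3% |

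The reference value is 5%. The SAP plans no between-arm test, so the last column is only a gauge of how misleading the picture could be. Neither f nor d is in the documents.

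**The case against.** Much of the case on the other side stands.

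- **Arm 1's setting is inferred.** No sentence says that Arm 1 takes BrainCheck inside the clinic on Days 8 and 21. It follows from the clinic-visit row, from the telephone row being limited to Days 4 and 11 and, for Day 8 only, from the footnote placing assessments before drug is dispensed. Subjects keep the iPad throughout, so home testing on a visit day is not excluded. This is a further reason to record the mode.
- **A remote visit need not mean testing alone.** The Arm 2 schedule separates remote visits (Days 8 and 21) from remote testing with no visit (Days 4 and 11), and a telemedicine visit implies staff contact. Whether staff watch the test is not stated.
- **Direction.** A reader might infer that supervised testing would flatter OXE-103. The documents do not support a sign: travel, examination, blood sampling and ECG on the same day could equally lower Arm 1's scores.
- **Questionnaires.** A reader might extend the point to PCSS, QOLIBRI and PGAS. These are self-reported in either setting, and any effect is probably smaller.
- **Missing data.** A reader might expect more missing control assessments on Days 4 and 11, because only Arm 1 is telephoned. Nothing in the documents shows this.
- **Primary time point.** The primary and secondary objectives run from baseline to Day 15, in clinic in both arms. Day 8 values can enter Day 15 results through carry-forward (SAP 6.10), and the ROC analysis may use an earlier day (SAP 6.8), but both concern PCSS responders, not BrainCheck.
- **Larger problems.** Part A is open-label, non-randomised and descriptive, and people who decline treatment or fail screening for it may become controls. SAP version 1.0 still describes Part A as randomised and placebo-controlled, which explains its silence here.

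What remains is that the schedule permits a setting difference by arm on two analysed days, and nothing records or handles it.

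**Conclusion.** The point holds for BrainCheck on Days 8 and 21 in Part A, and its severity is minor. On those days the plan allows the setting to differ by arm and compares the arms without regard to it, so the differences can mix treatment with testing conditions. On the assumed ranges (25% to 100% of controls remote, a shift of 0.1 to 0.5 SD) the distortion runs from 0.025 to 0.50 SD in either direction; the middle case of 0.15 SD is about a quarter of the 0.62 SD half-width. If every control attends in person, or if setting has no effect on the score, the distortion is zero.

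The documents do not support concluding that the Part A cognitive result is biased in favour of OXE-103, or that the Day 15 comparison is compromised by testing mode.

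**What to change.** 1. Add a field recording the mode at every BrainCheck assessment in both arms: in clinic supervised, remote with staff present, or alone.
2. In the SAP, base Part A between-arm BrainCheck contrasts on Days 4, 11, 15 and 44, when the schedule gives both arms the same setting.
3. Present Day 8 and Day 21 BrainCheck results by recorded mode, or as within-arm description only. Mode among controls is not assigned at random, so a breakdown by mode is descriptive.
4. Correct the arm label in the telemedicine sentence of the Recruitment section.

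The cost is one data field, some SAP wording, and less use of between-arm BrainCheck data at two visits that are not the primary time point. The SAP needs revision for the Part A redesign in any case. Moving Arm 1's Day 8 and Day 21 tests home would also equalise the setting, but those days would then differ from Arm 1's clinic baseline; with mode recorded and the contrasts limited as above, that trade is unnecessary.

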In the 39-week toxicity study (0; 300; 1000; 5000 µg/kg/day) evaluating OXE103 (SUN11031) SC administration in monkeys, no animals died, and doses up to 1000 µg/kg/day were well tolerated with no toxic signs observed. Local irritation was observed at the injection site and considered to be related to the dosing procedure and the vehicle (0.03 mol/L acetic acid buffer [pH 4.0] containing 10% sucrose and 1% benzyl alcohol). Antibody titers were below the lower limit of detection. However, incidences and/or grades of inflammation of the subcutaneous tissue and regeneration of the cutaneous muscle fiber were slightly greater in the 5000 µg/kg group than in the vehicle control group. The NOAEL was determined to be 1000 µg/kg/day.

Male and female rats treated with OXE103 (SUN11031) by SC administration for 13 weeks developed anti OXE103 antibody at the end of the dosing period which did not differ from control rats at the end of the recovery period.

No effects were observed on fertility in rats, on reproductive function in parental rats and maternal rabbits, or on embryo-fetal development in rats or rabbits by IV administration. In addition, no effects were observed on maternal rabbits and on embryo-fetal development in rabbits by SC administration. In an IV-dose study on pre- and postnatal development including maternal function in rats, a tendency to increase in body weights of live newborns

was noted at 300 µg/kg/day or more as pharmacological effects of OXE103 (SUN11031).

OXE103 (SUN11031) was not judged to be genotoxic. Although some results suggest that OXE103 may promote proliferation of selected cell types under experimental conditions, there is no clear evidence of tumor promoting potential in vivo.

In monkeys, a dose of 1000 µg/kg is approximately 4 fold higher than a clinical dose of 40 µg/kg twice daily based on body surface area. This may also be expressed as a systemic equivalent total daily exposure of approximately 28- and 12 fold for maximum plasma concentration (Cmax) and area under the plasma concentration time curve (AUC), respectively.

B. Clinical Overview

Safety, tolerability and pharmacokinetics of, SUN11031 (alternatively OXE103) has been evaluated in 9 clinical studies with the SC and IV routes of administration:

- 4 phase 1 clinical studies in healthy volunteers:
 - 3 in Japan (NA 1401, NA 1501, and NA 1502 – all IV administration) and
 - 1 in the US (ASBI 301 – SC and IV administration).
- 4 phase 2 clinical studies:
 - 1 study in subjects with eating disorders conducted in Japan (NA 2601 – IV administration),
 - 1 study in subjects with cachexia associated with CHF conducted in Poland (ASBI 303 – SC administration),
 - 1 study in subjects with cachexia associated with COPD conducted in the US (ASBI 304 – SC administration), and
 - 1 multinational study in subjects with cachexia associated with COPD (ASBI 307 – SC administration).
- 1 phase 3 clinical study:
 - in subjects with eating disorders in Japan (NA 3801 – IV administration).

SUN11031 has been administered as either an IV bolus or IV infusion in 6 clinical studies (NA 1401, NA 1501, NA1502, ASBI 301, NA 2601, and NA 3801) and as an SC injection in 4 clinical studies (ASBI 301, ASBI 303, ASBI 304, and ASBI 307).

Subcutaneous injections of SUN11031 at doses up to 45.5 µg/kg once daily and 22.7 µg/kg bid for up to 7 days, have been administered to healthy subjects. Subcutaneous doses of SUN11031 10 µg/kg bid have been administered to subjects with cachexia associated with CHF (ASBI 303; 6 subjects; up to 14 days) and up to 20 µg/kg bid have been administered to subjects with cachexia associated with COPD (ASBI 304 [during which 9 subjects were administered 10 µg/kg bid and 8 subjects were administered 20 µg/kg bid] for up to 21 days and ASBI 307 [during which a total of 75 and 76 subjects were administered 20 and 40 µg/kg bid SUN11031, respectively]) for up to 3 months.

This statistical analysis plan (SAP) provides details on the study design, outcome measures and data analyses planned for the exploratory study of ghrelin (OXE-103) in subacute and acute concussion management that is being conducted at the University of Kansas Health System Center for Concussion Management (CCM). The outcome measures and data analyses specified in this SAP supersede any specified in the study protocol, if differences exist.

Any deviations from this plan will be documented in the clinical study report, and will include timing of changes in relation to unblinding of the study.

Pharmacokinetic, anti-ghrelin antibody and/or biomarker samples may be collected for future use and any data analysis will be the subject of a separate SAP.

2. Study Design

This subacute and acute concussion management study will be conducted as a randomized, single center, double-blind, placebo-controlled, parallel group design in two distinct parts. In Part A, subjects will be recruited from the University of Kansas Health System CCM clinics which include Neurology, Sports Medicine, and Neurosurgery/Physical Medicine and Rehabilitation. Subjects who provide written informed consent and satisfy enrollment criteria at the end of a 7-day screening period will be randomized in a 1:1 manner to either the OXE-103 or placebo treatment groups. In Part B, subjects will be recruited from the emergency department and enrolled within 24 hours of injury. Treatments will be self-administered subcutaneously twice daily during a 14-day treatment period; the OXE-103 group will receive 40 µg/kg with each dose.

For Part A, clinic visits will be conducted at the start of Screening (Day -7), Randomization (Day 1), Day 8, End of Treatment (Day 15), 1 week after the end of treatment (Day 21) and End of Study (Day 44).

Phone contacts will be done during Screening (Day -3) and during treatment (Days 4 and 11). Part B subjects will follow the same schedule except that there will be no screening visit or phone contact.

Outcomes for the investigation of the effect of OXE-103 will be based on self-reported symptom scoring, quality of life questionnaires, computerized cognitive testing assessing executive function, memory and processing speed, and accelerometer-based balance scoring. Safety assessments will include collection of adverse events, clinical laboratory samples, electrocardiograms (ECGs), vital signs including body weights, suicide screening and physical/neurological examination findings.

3. Study Objectives

The primary objective of this study is to describe the change in symptom burden of subacute or acute concussion for the two treatment groups in each part, as measured by the change from baseline to Day 15 in the Post-Concussion Symptom Score questionnaire (PCSS) total score, total number of symptoms and total score for the 4 most bothersome symptoms (4MBS, as identified on Day 1). Improvements of $\geq 20\%$ will be considered clinically meaningful.

The secondary objectives are to:

- Describe the change in quality of life for the two groups in each part as measured by the change from baseline to Day 15 in the Quality of Life after Brain Injury (QOLIBRI) total score and Patient Global Assessment of Status Visual Analog Scale (PGAS VAS).
- Describe changes in cognitive performance for the two groups in each part as measured by the change from baseline to Day 15 in the BrainCheck composite score.

Exploratory objectives of the study are to:

- Describe the correlation between the change in symptom burden and quality of life during the treatment period for each group in each part.
- Describe changes in symptom burden and quality of life at different time points for the two groups in each part.

4. Sample Size

The exploratory nature of this study is such that it is not powered to yield statistically significant outcomes, but will allow detection of trends within subjects and between groups within each part, will support comparison with standard tests of neurocognitive functions, and will provide sample size estimates for future studies of individuals with acute or persistent concussion related symptoms.

The study will enroll a maximum of 50 subjects in each part, but may stop recruiting if each group has at least 20 participants who have completed the study.

5. Outcome Measures

